5.2 Patient Disposition and Data Sets Analyzed

The number of subjects included in each of the ITT, PP and safety populations will be summarized for each treatment group and overall. The number and percentage of subjects randomized and treated will be presented. Subjects who completed the study and subjects who withdrew from study prematurely will also be presented with a breakdown of the reasons for withdrawal by treatment group for the ITT, PP and safety populations.

5.3 Protocol Violations/Deviations

Major protocol deviations are those that are considered to have an effect on the analysis. A list of potential major protocol deviations will be generated programmatically from the data captured before the clean file meeting. The clinical monitors of the study will review the list and the finalisation of the major protocol deviations will be done at the clean file meeting.

The number of patients with major protocol deviations will be summarized per treatment group.

Major protocol deviations

STATISTISKA KONSULTGRUPPEN		Statistical Analysis Plan	
Protocol: The prophylactic effect of Levosimendan in reducing acute kidney injury postoperatively in pediatric patients undergoing corrective heart surgery		Protocol No: MiLe-1	Version: 1.0 Page 15 of 17

- 1) Inadequate informed consent
- 2) Inclusion or exclusion criteria are not met
- 3) Unreported serious adverse events
- 4) Improper randomization
- 5) Improper breaking of the blind
- 6) Baseline serum Creatinine missing
- 7) Serum Creatinine postoperative day 1 and 2 are both missing (primary outcome)
- 8) Materially inadequate record keeping
- 9) Intentional deviation from protocol or GCP

Minor protocol deviations

- 1) Study drug protocol not followed appropriately
- 2) One or more of following blood samples are missing or mishandled: Serum Creatinine postop day 1 or 2. Any of plasma samples T0 – T5
- 3) 28 days follow-up information (28 days outcome) is missing

5.4 Screening, preoperative data and Preop samples taken in OR from art and cvc line

Demographics and baseline characteristics will be summarized by treatment group for the ITT and PP populations and analyzed according to the methods described in section “General Methodology” above.

5.5 Efficacy Analyses

5.5.1 Primary Efficacy Analysis

Logistic regression of AKI (50% increase in corrected creatinine within 48 hours) with treatment group independent variable will be used for the primary outcome. If differences in corrected creatinine at baseline differs between groups adjustment for baseline corrected creatinine will be made by adding baseline creatinine as an independent variable. The analysis will be two sided and with alpha 0.05.

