## **1. INTRODUCTION**

### **1.1 The importance of acute kidney injury**

Acute renal failure (ARF), which recently has been refined and defined as acute kidney injury (AKI), is a common and serious condition in critically ill pediatric and adult patients. Due to lack of standard definition of ARF the reported incidence of AKI has varied considerably, namely between 5 and 50% of critically ill patients, both children and adults. The morbidity and mortality of AKI is unacceptably high. The reported mortality rates of about 40-50% in dialysis-dependent AKI, demonstrates the seriousness of the condition. AKI is an independent factor for mortality in critically ill patients, meaning that the patients do not simply die with AKI but also from AKI. The treatment is supportive in addition to reversing the underlying causes. The supportive measures include optimizing fluid and cardiorespiratory status, avoiding nephrotoxic medications and renal replacement therapy [2].

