### **2.2 Primary endpoint**

AKI is usually defined as 50% increase in creatinine within 48 hours. Accordingly, the primary outcome in this study is the postoperative creatinine levels which will be measured according to table 1.

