## **10. STATISTICAL METHODS AND SAMPLE SIZE**

### **10.1 Sample size calculation**

The number of patients needed for the study is based on a 20% reduction in creatinine in the Levosimendan group compared with the Milrinone group in the day after stopping the infusion of Levosimendan/Milrinone (second postoperative day). The power of study is set on 80 %.

The study will contain two groups; Levosimendan (n=35) and Milrinone n=35). Patients in the Levosimendan group will receive Levosimendan as inotrope agent and patients in the Milrinone group will receive Milrinone as inotrope agent. Patients will randomly be assigned to either group. The caregivers (physicians, nurses and nurse-assistants) will be blinded for the study. The same infusion rate and total volume of Levosimendan and Milrinone will be applied to both groups.

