### **10.2 Statistical analysis**

Analysis of data will be performed by a professional statistician. T-test for independent groups will be used for primary outcome. Descriptive statistics will be applied on the secondary outcomes including 30-days mortality, length of hospital stay and kidney function 5 days after start of infusion of Milrinone/Levosimendan. Additionally, clinical data (fluid balance, length of surgery, length of CPB, length of mechanical ventilation postoperatively, length of vasoactive therapy, number of vasoactive medications, total amount of infused vasoactive drugs, hemodynamic parameters) will be registered and analyzed. Univariate analyses will be used where needed. Multivariable regression analysis will be used to identify association between the occurrences of AKI (based on creatinine results) and the measured clinical variables.

Clinical Study Protocol  
Study Code: MiLe-1  
Drug Substance: Levosimendan  
EudraCT No: 013-003105-25  
Date

Other statistical methods might be used in an exploratory fashion but no formal inference will be made.

Safety and tolerability data will be summarized descriptively by treatment and presented in tabular and/or graphical form. All adverse event data will be listed individually and summarized using MedDRA terminology.

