1 STUDY DETAILS

1.1 Study Objectives

The aim of the study is to assess the ability of Levosimendan to reduce the postoperative acute kidney injury in pediatric patients undergoing surgery for congenital heart disease (CHDs).

The primary objective of this study is to investigate the preventive effect of Levosimendan on postoperative acute kidney injury in pediatric patients undergoing surgery for their CHDs. Creatinine at the second postoperative day will be the primary endpoint.

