1.4 Sample Size

The number of patients needed for the study is based on a 20% reduction in serum creatinine in the Levosimendan group compared with the Milrinone group in the day after stopping the infusion of Levosimendan/Milrinone (second postoperative day). The power of study is set on 80 %.

The study will contain two groups; Levosimendan (n=35) and Milrinone n=35). Patients in the Levosimendan group will receive Levosimendan as inotrope agent and patients in the

STATISTISKA KONSULTGRUPPEN		Statistical Analysis Plan	
Protocol: The prophylactic effect of Levosimendan in reducing acute kidney injury postoperatively in pediatric patients undergoing corrective heart surgery		Protocol No: MiLe-1	Version: 1.0 Page 7 of 17

Milrinone group will receive Milrinone as inotrope agent. Patients will randomly be assigned to either group. The caregivers (physicians, nurses and nurse-assistants) and the investigators will be blinded for the study drug. The same infusion rate and total volume of Levosimendan and Milrinone will be applied to both groups.

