4.4 Efficacy Variables/Endpoints

4.4.1 Primary endpoint

AKI_(48 hours) is defined as 50% increase in corrected creatinine within 48 hours. AKI_(48 hours) is calculated using screening creatinine (uncorrected) compared to 24 and 48 hours corrected creatinine.

Corrected creatinine [(creatinine (μmol/ml)/1000 x [1 + (fluid balance (L)_(+24 hours) / (weight (kg x 0.6)))] only calculated for day 1-3. For example for day 1 the Fluid balance measured at day 2 will be used. If negative values in fluid balances, fluid balance is set to 0.

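### The SAP tests binary AKI within 48 hours as primary, but still names day-2 creatinine as primary in section 1.1 and carries an 80% power that was set for creatinine

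*SAP*

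**What the plan says.** The protocol plans a continuous primary outcome. Section 2.2 says "the primary outcome in this study is the postoperative creatinine levels which will be measured according to table 1", and section 10.2 says "T-test for independent groups will be used for primary outcome". Section 10.1 bases the number of patients on a "20% reduction in creatinine in the Levosimendan group compared with the Milrinone group in the day after stopping the infusion", with 80% power and 35 per arm.

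The SAP is split:

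- SAP 1.1 (Study Objectives): "Creatinine at the second postoperative day will be the primary endpoint".
- SAP 1.4 (Sample Size): "The number of patients needed for the study is based on a 20% reduction in serum creatinine". The 80% power and 35 + 35 are carried over from the protocol; the total of 70 stands in SAP 1.2.
- SAP 4.4.1 (Primary endpoint): AKI within 48 hours, a yes/no variable that "is calculated using screening creatinine (uncorrected) compared to 24 and 48 hours corrected creatinine".
- SAP 5.5.1, on how the primary test is done, states: "Logistic regression of AKI (50% increase in corrected creatinine within 48 hours) with treatment group independent variable will be used for the primary outcome".
- SAP 4.4.3 lists creatinine and corrected creatinine among the secondary endpoints, and SAP 5.5.2 assigns the t-test to secondary continuous outcomes.
- SAP 7 (Changes of Analysis from Protocol) contains only the template's instruction to list changes. None is listed.

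**The concern.** Between protocol and SAP the primary endpoint went from a continuous variable compared by t-test to a dichotomy analysed by logistic regression, while the sample-size section stayed as it was. Two things follow.

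First, the SAP names two primary endpoints on different scales, and no dated entry shows when the change was made relative to lock and unblinding. If the two endpoints disagree, the choice of headline result could look as though it followed the data.

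Second, the only power figure in the plan belongs to the endpoint that is no longer tested as primary. If it is read as the power of the AKI analysis, a non-significant result would be taken as stronger evidence of no effect than 35 per arm can give.

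**Working it through.** **Inputs from the documents.** 35 per arm, 1:1, 80% power, 20% relative reduction in creatinine (SAP 1.4; protocol 10.1); two-sided 0.05 (SAP 5.1). Neither document gives an SD or mean for creatinine. The only AKI incidence is in protocol 1.1, "namely between 5 and 50% of critically ill patients, both children and adults", which describes critically ill patients in general and not elective infant surgery. It serves here only as a range for assumed control rates.

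**1. The plan's own figure.** With no SD, 35 per arm can only be solved backwards. From n = 2(1.960 + 0.842)² (SD/δ)² with n = 35 and δ = 20% of the control mean:

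SD = 0.20 × √(35/2) / 2.802 = 0.299, about 30% of the control mean (29.4% with the noncentral t).

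The figure is thus attainable for creatinine but cannot be confirmed. Needed n per arm is 25 at an SD of 25%, 36 at 30% and 63 at 40%.

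**2. What 35 per arm can detect for AKI.** Exact binomial enumeration over all 35 v 35 outcomes, rejecting when the likelihood-ratio (LR) chi-square for treatment exceeds its 5% point. The relative reduction is 1 minus (test rate / control rate).

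| Assumed control AKI | Highest test-arm rate with 80% power | Relative reduction |
|---|---|---|
| 50% | 19.5% | 61% |
| 40% | 12.0% | 70% |
| 30% | 5.9% | 80% |
| 20% | 1.9% | about 90% |
| 10% | not reachable; 69% power with no AKI in the test arm | |
| 5% | not reachable; 25% power with no AKI in the test arm | |

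Halving AKI from 30% to 15% has 34% power. A 20% relative reduction in AKI has about 8% to 13% power at control rates of 10% to 50%.

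**3. Dependence on the test.** SAP 5.5.1 does not name the test of the treatment term. The score test gives 1.7, 5.8, 11.5 and 19.1% in place of 1.9, 5.9, 12.0 and 19.5%. At low rates the difference is large: maximum power at a 10% control rate is 47% by the score test against 69% by LR, and at 5% it is 10% against 25%. The LR test exceeds its nominal level there (actual type I error 6.9% at a 10% rate and 8.9% at 5%), so its low-rate powers are flattered.

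**4. Linking the two scales.** Suppose the log creatinine ratio is normal and treatment shifts it by ln(0.8) = −0.223. With d = 0.223/SD and control rate p, the test-arm AKI rate is Φ(Φ⁻¹(p) − d).

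| Assumed log-SD | d | t-test on the log ratio | AKI, LR, control rate 10% to 50% |
|---|---|---|---|
| 0.20 | 1.116 | 99.6% | 55% to 94% |
| 0.25 | 0.893 | 96% | 45% to 82% |
| 0.30 | 0.744 | 87% | 38% to 69% |
| 0.40 | 0.558 | 63% | 27% to 46% |

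At a 5% control rate AKI power is 16% to 23% across these SDs. If d took the value that gives a t-test 80% power at 35 per arm (0.679), AKI power would be 34% to 61% at control rates of 10% to 50%. That is a further assumption, because the SD behind the sample size refers to creatinine on one day and not to a ratio to baseline.

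**The case against.** The operative parts of the SAP agree with each other. Sections 4.4.1, 5.5.1 and 5.5.2 and Table 14.3.1 point to AKI, and the seventh major deviation in SAP 5.3 (creatinine missing on both day 1 and day 2) fits a 24-or-48-hour AKI variable. The contrary text is one sentence in SAP 1.1. Nor is AKI foreign to the protocol: section 2.2 opens with the 50% rise within 48 hours, section 3 identifies AKI cases by a rise above 50%, and the hypothesis in section 1.7 concerns incidence. SAP 1.4 says openly that its calculation rests on creatinine. Finally, the comparison in step 4 uses a t-test on the log ratio, which neither document plans, and some AKI cells exceed 80% (84% to 94% at log-SD 0.20 with control rates of 30% to 50%; 82% at log-SD 0.25 with 50%).

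Much of this stands. The intended test is clear, AKI is a legitimate endpoint, and power below 80% is likely but not proved. Step 4 also simplifies: the real endpoint takes either of two days and uses fluid-corrected values. But protocol 2.2 goes on to make creatinine levels the primary outcome, with a t-test in 10.2. None of these points corrects SAP 1.1, supplies an AKI assumption, or fills SAP 7.

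**Conclusion.** The concern holds, and should be settled before database lock. The SAP contradicts itself on the primary endpoint, does not record the departure from the protocol, and gives no power basis for the test it calls primary. These three facts rest on the text alone.

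The size of the power gap is illustrative because every AKI rate and SD is assumed. At control rates of 20% to 50%, 80% power requires relative reductions of roughly 90% down to 61%. At 10% or below it is out of reach. Under the log-shift model AKI power ranges from about 16% (5% control rate) to 94% (50% control rate, log-SD 0.20), and in every scenario run at control rates of 10% to 50% it was below that of the continuous analysis under the same assumptions.

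**What to change.** Name one primary endpoint in SAP 1.1, 1.4, 4.4.1 and 5.5.1. The smallest change keeps AKI within 48 hours as primary:

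- Correct SAP 1.1.
- Add to SAP 1.4: *The 80% power refers to a 20% reduction in serum creatinine on postoperative day 2. For AKI within 48 hours, assuming a control rate of [sponsor's value] and a target rate of [sponsor's value], 35 per group give [resulting value] power for the [named] test in the logistic regression.*
- Record the change of endpoint and analysis in SAP 7, with its date relative to lock and unblinding.

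The alternative is to restore day-2 creatinine as primary, with AKI as key secondary. The SAP would then have to say which creatinine is meant (SAP 4.4.3 lists raw, corrected and age-differentiated corrected values) and give the SD behind 35 per arm.

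Either route is SAP wording, with no new patients or data. The first probably means stating a less favourable power; the second gives up AKI as the headline endpoint.

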5.5.2 Secondary Efficacy Analyses

Complementary analyses of the primary analysis will be made up to 72 hours and also one analysis up to 96 hours in the same fashion as the primary analysis.

Secondary variables will be presented at each timepoint and changes from baseline (screening, pre-op) will be calculated where applicable. T-test for independent groups will be used for secondary continuous outcomes if the data not is clearly non-normal distributed. If baseline values differs between groups adjustment for baseline values will be made using a covariance analysis will be made. If the outcome is clearly non normal distributed Fishers non parametric permutation test will be used instead of t-test.

Categorical (no/yes) variables will be analysed between groups by using Fisher exact test.

Univariable and multivariable logistic regression analysis will be used to identify association between the occurrences of AKI (based on creatinine results) and the measured clinical variables.

STATISTISKA KONSULTGRUPPEN		Statistical Analysis Plan
Protocol: The prophylactic effect of Levosimendan in reducing acute kidney injury postoperatively in pediatric patients undergoing corrective heart surgery	Protocol No: MiLe-1	Version: 1.0
		Page 16 of 17

5.5.3 *Exploratory Efficacy Analyses*

Selected correlation analyses will be performed between secondary variables/outcomes.

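### SAP 5.5.1 leaves the estimator, test statistic and zero-event fallback unspecified for the primary AKI logistic regression in 35 infants per arm, and the usual choices misbehave if AKI is uncommon

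*SAP*

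**What the plan says.** The primary endpoint is binary (SAP 4.4.1): "AKI_(48 hours) is defined as 50% increase in corrected creatinine within 48 hours". SAP 5.5.1 gives the analysis: "Logistic regression of AKI (50% increase in corrected creatinine within 48 hours) with treatment group independent variable will be used for the primary outcome". It adds baseline creatinine as a covariate if the groups differ at baseline, and sets the level: "The analysis will be two sided and with alpha 0.05". SAP 5.5.2 repeats the analysis up to 72 h and up to 96 h in the same way. SAP 5.1 names SAS 9.4 and no model options.

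For other yes/no variables, SAP 5.5.2 uses a small-sample method: "Categorical (no/yes) variables will be analysed between groups by using Fisher exact test".

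The sample size (SAP 1.4) is "The study will contain two groups; Levosimendan (n=35) and Milrinone n=35", "based on a 20% reduction in serum creatinine in the Levosimendan group compared with the Milrinone group". No AKI rate enters it. The only AKI frequency in either document is in Protocol 1.1, where reported incidence is "namely between 5 and 50% of critically ill patients, both children and adults".

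**The concern.** Logistic regression is usually fitted by maximum likelihood and tested by either the Wald or the likelihood-ratio statistic. In samples of this size the choice matters when events are few.

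If one arm has no AKI, the maximum-likelihood log odds ratio diverges, its standard error explodes, and the Wald test returns a p-value near 1 however many events the other arm has. A near-complete protective effect is then the result the analysis handles worst. The likelihood-ratio test still gives a p-value, but rejects too often at low rates.

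Since the SAP does not say which applies, the primary conclusion could depend on a choice made after the data are seen. Switching methods on meeting an empty cell, or a Wald p just above 0.05, would be data-driven.

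**Working it through.** **The plan's own figure.** The 35 per arm concerns a mean difference in creatinine, and no SD is given, so it can only be back-solved. With n = 2(1.96 + 0.8416)² CV² / 0.20² = 392.4 CV², setting n = 35 gives CV = √(35/392.4) = 0.299. This says nothing about power for the AKI endpoint.

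**Inputs.** 35 per arm and two-sided 0.05 come from SAP 1.4 and 5.5.1. All AKI rates below are assumptions. No covariate is included.

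**Chance of an empty arm.** P(no AKI in an arm) = (1 − p)³⁵. With the same risk p in both arms, P(at least one empty) = 2q − q², where q = (1 − p)³⁵:
- p = 5%: q = 0.166, giving 30%
- p = 10%: q = 0.0250, giving 4.9%
- p = 20%: q = 0.0004, giving 0.08%

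If levosimendan halves the risk, the chance is 51% at a 5% control rate, 19% at 10%, 2.5% at 20% and 0.3% at 30%.

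**An empty arm: 0/35 v 6/35.** Maximum likelihood has no finite estimate and Wald p is about 1. For a two-arm comparison, Firth's method amounts to adding 0.5 to each cell. The odds ratio is (0.5 × 29.5)/(35.5 × 6.5) = 0.064. The penalised likelihood-ratio statistic, with expected cells 3.5 and 32.5 in each arm, is 2[0.5 ln(0.5/3.5) + 35.5 ln(35.5/32.5) + 6.5 ln(6.5/3.5) + 29.5 ln(29.5/32.5)] = 6.66, p = 0.010. Fisher gives 0.025 and the unpenalised likelihood-ratio test 0.003. A direct fit of a similar table, 0/35 v 8/35, failed to converge: log odds ratio −30.6, SE about 1.35 million.

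**No empty cell: 1/35 v 7/35.**
- Wald: ln[(1 × 28)/(34 × 7)] = −2.140; SE = √(1 + 1/34 + 1/7 + 1/28) = 1.099; z = −1.947, p = 0.052.
- Likelihood ratio: 2[ln(1/4) + 34 ln(34/31) + 7 ln(7/4) + 28 ln(28/31)] = 5.64, p = 0.018.
- Firth: the same form with 0.5 added to each cell gives 4.94, p = 0.026.

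At 2/35 v 8/35 the three p-values are 0.057, 0.035 and 0.044.

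**Operating characteristics.** All 36 × 36 possible tables were enumerated and binomial probabilities summed where p < 0.05. For Wald, tables with an empty cell count as non-significant.

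Type I error:

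| Common risk | Wald | Likelihood ratio | Firth | Fisher |
|---|---|---|---|---|
| 5% | 0.02% | 8.9% | 3.3% | 0.3% |
| 10% | 0.7% | 6.9% | 4.3% | 1.3% |
| 20% | 4.1% | 5.4% | 4.7% | 2.5% |

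Power:

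| Milrinone v levosimendan AKI | Wald | Firth |
|---|---|---|
| 20% v 0% | 0% | 94% |
| 20% v 5% | 22% | 47% |
| 20% v 10% | 14% | 20% |
| 30% v 15% | 31% | 32% |
| 40% v 20% | 44% | 44% |

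**The case against.** A reader might infer several stronger things that the documents do not support.

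**That the SAP commits to a maximum-likelihood Wald test.** It does not; it says only logistic regression. A likelihood-ratio test gives a p-value even with an empty arm. This stands, and it makes the fault one of specification. It does not remove the problem, because the two ordinary readings err in opposite directions at low rates, and with an empty arm the maximum-likelihood odds ratio is still not finite.

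**That 5-50% is this trial's expected AKI range.** Protocol 1.1 reports it for critically ill children and adults and attributes the spread to the lack of a standard definition. There are reasons to expect a rate above the bottom of that range. All infants undergo bypass, which Protocol 1.2 links to AKI, and SAP 4.4.1 compares fluid-corrected postoperative creatinine with uncorrected baseline and sets negative balances to zero, so the correction can only add events. This stands: the low rates are possibilities, not predictions.

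**That the choice of test explains the low power at low rates.** For modest effects it mostly does not. With 5% halved, Firth itself has about 4% power; a normal-approximation calculation needs 906 per arm there, and 199 per arm for 20% halved. The largest gap with events expected in both arms, 20% v 5%, assumes a 75% relative reduction, which neither document proposes.

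**That the loss extends well beyond empty arms.** It extends only a little. Against Firth, Wald needs one more event in the other arm when an arm has one or two events, and none more at three. Of the 25-point gap at 20% v 5%, 15.6 points come from empty cells and 9.1 from tables with one or two events in an arm. Against Fisher, Wald loses nothing at one or two events.

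Finally, Firth is not the only defensible method. Exact logistic regression or a prespecified Fisher fallback would also close the gap in the plan. Fisher is more conservative here (13% power against Firth's 20% at 20% v 10%) and cannot carry the baseline creatinine covariate that SAP 5.5.1 provides for.

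**Conclusion.** The point holds as a specification gap with real consequences when AKI is uncommon. The primary analysis names no estimator, test statistic or zero-event fallback; Wald is far too conservative and the likelihood-ratio test too liberal at 5-10% AKI, and the two can give opposite verdicts on the same data. Firth kept type I error below 5% and had power at least equal to Wald in every scenario checked.

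The size depends on an AKI rate that the documents do not give. The gain over Wald is 25 points at 20% v 5%, about 7 at 20% v 10%, about 1 at 30% v 15%, and nil at 40% v 20%. If both arms are at about 30-40%, nothing changes. The figures assume 35 analysable infants per arm and no covariate; missing 24 h and 48 h creatinine would reduce that number. Whether 70 patients suffice for a binary endpoint is a separate question that this change does not answer.

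**What to change.** In SAP 5.5.1, before unblinding, specify Firth penalised-likelihood logistic regression of AKI on treatment, tested by the penalised likelihood-ratio test, with a profile-likelihood 95% confidence interval for the odds ratio. State that the 72 h and 96 h analyses in SAP 5.5.2 use the same method, and that baseline creatinine, where included, enters the same model. Record the change in SAP section 7.

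The cost is one sentence and one option in the SAS logistic procedure, with no new data or patients. The downside is slight shrinkage of the odds ratio towards 1.

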4.4.3 Secondary endpoints Follow up postop days 1-4

Fluid balance

- Fluid balance ((ml)
- Urine (ml)
- Weight (g)
- %FO (fluid balance (ml)/1000_(+24 hours) /preop weight (kg)) x 100. For example for day 1 the Fluid balance measured at day 2 will be used. If a negative fluid balance set %FO to 0.
- Cumulative %FO (day 1+2, day 1+2+3, day 1+2+3+4)

STATISTISKA KONSULTGRUPPEN		Statistical Analysis Plan	
Protocol: The prophylactic effect of Levosimendan in reducing acute kidney injury postoperatively in pediatric patients undergoing corrective heart surgery		Protocol No: MiLe-1	Version: 1.0 Page 12 of 17

- Peritoneal Dialysis day 1 and day 2 from Status and medication_1 and Status and medication_2

Morning lab results (Postop day 1 is under hemodynamics_1, etc.)

- Hb (g/L)
- Hct
- Leucocytes ($\times 10^9/L$)
- Trombocytes ($\times 10^9/L$)
- C R P (mg/L)
- Albumin (g/L)
- Creatinine ($\mu\text{mol}/L$)
- Corrected creatinine [$(\text{creatinine } (\mu\text{mol}/L) \times [1 + (\text{fluid balance } (L)_{(+24 \text{ hours})} / (\text{weight } (\text{kg}) \times 0.6)])]$ only calculated for day 1-3. For example for day 1 the Fluid balance measured at day 2 will be used. If negative values in fluid balances, fluid balance is set to 0.
- Corrected creatinine (age differentiated), same as above but (in the formula) using 0.75 for infants younger than 5 months and 0.6 for infants/adults older than 5 months.
- AKI_(72 hours) and AKI_(96 hours) in same fashion as in primary endpoint
- AKI stage at 48 (24 and 48), 72 and 96 hours.
 - Stage 0 (no AKI, corrected creatinine up to 1.49 times screening creatinine)
 - Stage 1 (corrected creatinine 1.5-1.99 times screening creatinine)
 - Stage 2 (corrected creatinine 2-2.99 times screening creatinine)
 - Stage 3 (corrected creatinine 3 (or more) times screening creatinine or need of dialysis)
- eGFR Creatinine (calculated value from CRF)
- Cystatin C (mg/L)
- eGFR Cystatin C, calculated using formula $91 \times \text{Cystatin C } (\text{mg/L})^{-1.213}$
- Urea (mmol/L) Use value in database (no recalculation is needed), in CRF the unit stands as $\mu\text{mol}/L$ but it is actually mmol/L.
- Combined eGFR (mL/min per 1,73 m²)
 - $39.1 \times [\text{height } (\text{m})/\text{Serum creatinine } (\text{mg/dl})]^{0.516} \times [1.8/\text{Cystatin C } (\text{mg/L})]^{0.294} \times [30/\text{Urea } (\text{mg/dl})]^{0.169} \times [1.099]^{\text{male}} \times [\text{height } (\text{m})/1.4]^{0.188}$

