5 STATISTICAL METHODOLOGY

5.1 General Methodology

All baseline, efficacy and safety variables will be summarized by treatment group. Continuous variables will be presented with mean, standard deviation (SD), Median, minimum, maximum and number. Categorical variables will be presented as number and percentage (%).

All tests will be two-tailed and conducted at 0.05 significance level. All analyses will be performed by using SAS® v9.4 (Cary, NC).

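### SAP 5.5.1 adds baseline creatinine to the primary AKI model only if the arms differ at baseline, with no criterion or decision time, so the primary model is not fixed in advance

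*SAP*

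**What the plan says.** - **Default model (SAP 5.5.1).** Logistic regression of AKI "with treatment group independent variable will be used for the primary outcome", two-sided at 0.05.
- **Conditional change (SAP 5.5.1).** If "corrected creatinine at baseline differs between groups adjustment for baseline corrected creatinine will be made by adding baseline creatinine as an independent variable". What counts as a difference is not stated, nor when or by whom it is judged.
- **Baseline data (SAP 5.4 and 5.1).** Baseline characteristics are summarised for the ITT and PP "populations and analyzed according to the methods described in section" 5.1. That section lists summary statistics and adds: "All tests will be two-tailed and conducted at 0.05 significance level". It names no between-arm test of baseline variables and does not link one to the choice of model.
- **AKI reference value (SAP 4.4.1).** "AKI_(48 hours) is calculated using screening creatinine (uncorrected) compared to 24 and 48 hours corrected creatinine". The fluid correction is "only calculated for day 1-3. For example for day 1 the Fluid balance measured at day 2 will be used", so it covers postoperative days only.
- **Reach of the rule (SAP 4.4.3 and 5.5.2).** The later endpoints are "AKI_(72 hours) and AKI_(96 hours) in same fashion as in primary endpoint". There is a complementary analysis to 72 hours and "one analysis up to 96 hours in the same fashion as the primary analysis". SAP 5.5.2 repeats the conditional adjustment, as analysis of covariance, for continuous secondary endpoints.
- **No fallback.** Protocol 10.2 names a t-test for the primary outcome and no covariate rule. SAP 7 holds only an instruction to list changes.

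**The concern.** Two primary models are possible, and the SAP does not say what decides between them. Comparing the arms at baseline needs data split by group, and nothing ties the decision to a point before unblinding. By contrast, SAP 3.1.2 ties the per-protocol set to the Clean File meeting before database lock.

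The trigger cannot be programmed as written, because it refers to a corrected baseline value that SAP 4.4.1 does not define. This looks like a wording slip, but it has to be resolved before the rule can be applied.

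The trigger is also the wrong one. In a randomised trial a baseline difference is chance. Adjustment helps when the covariate predicts the outcome, and screening creatinine is the denominator of the ratio that defines AKI. At stake are which p-value counts as primary and, if baseline is prognostic, some power.

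**Working it through.** **The plan's own figure.** SAP 1.4 gives 35 per arm, a 20% creatinine reduction and 80% power, but no SD. Solving the two-sided 0.05 normal formula for the coefficient of variation gives CV = 0.20 × √(35/2) / (1.960 + 0.842) = 0.299 (0.294 with the exact t-test). The stated N cannot be reproduced without that missing input. It also concerns mean creatinine, not the AKI proportion. The log-SD range used below, 0.20–0.40, brackets it.

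**How often a difference would be declared.** With 35 per arm, the difference in baseline means has standard error √(2/35) = 0.239 SD. Under randomisation alone:

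| Possible criterion | Fires in |
|---|---|
| p<0.05 | 5% of trials |
| p<0.20 | 20% |
| difference >0.3 SD | 21% |
| difference >0.2 SD | 40% |
| difference >0.1 SD | 68% |

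The unstated criterion therefore decides how often the model changes.

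**Does screening creatinine predict AKI?** Let r be the correlation of log pre- and postoperative creatinine, and s the ratio of their SDs (post/pre). The correlation of log baseline with the log ratio is (rs − 1)/√(1 + s² − 2rs). At s = 1 this is −0.59, −0.50 and −0.39 for r = 0.3, 0.5 and 0.7. It is zero when rs = 1, and +0.28 at r = 0.8, s = 1.6. An association is likely but not certain.

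**Simulations (N = 70; all inputs below assumed except the 20% reduction).**
- **A:** creatinine model with 20 settings, 20,000 trials each under the null and under the 20% reduction. Control AKI 20–40%, r 0.3–0.8, s 1.0–1.6, stratified allocation, likelihood-ratio tests. Monte Carlo SE is about 0.15 points (null) and 0.35 points (power). The fluid correction is absorbed in r and s.
- **B:** direct logistic model, 20,000 trials per setting, Wald tests. AKI rate 20–50%, odds ratio per baseline SD of 1, 1/2 or 1/3.
- **C:** smaller runs, 8,000–10,000 trials per setting, which also counted disagreement only where the trigger fires.

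*Mechanical rule.* Type I error in A is 3.9–5.5% with a p<0.05 trigger and 3.6–5.5% with p<0.20. It is 3.3–4.6% in B (triggers 0.05 to 0.20) and 4.2–6.0% in C. Power in A is within 0.3 points (p<0.05) or 1.2 points (p<0.20) of the unadjusted model. The largest gap in B is 60.8 − 58.8 = 2.0 points (p<0.20).

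*Disagreement on significance under the 20% reduction.* Over all trials, 3–16% in A and 2–17% in C. As a share of all trials in which the trigger also fires (C):
- p<0.05: about 0.3–1.7%
- p<0.20: about 0.8–6.0%
- difference >0.2 SD: about 3.6–9.8%

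Dividing by the firing rate, among trials where the rule would switch models the results disagree in about 0.3/5 = 6% to 1.7/5 = 34% (p<0.05), or 0.8/20 = 4% to 6.0/20 = 30% (p<0.20).

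*Smaller of the two p-values.* Type I error is 5.5–7.5% in A and up to 8.2% in C. In B it is 5.1–6.4% if baseline predicts AKI and 4.6–5.0% if it does not.

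*Always adjusting against the p<0.05 rule.* Type I error in A is 4.3–5.8%. Nominal power changes by +0.2 to +7.9 points. With each test's critical value set to give exactly 5% under its own null (size-matched), the change is −1.7 to +6.6. Examples from A with control AKI 30%, log-SD 0.30, s = 1 and one postoperative value:

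| r | Power, rule v always: nominal | Size-matched |
|---|---|---|
| 0.3 | 41.4% v 48.7% | 44.5% v 49.4% |
| 0.5 | 52.5% v 58.3% | 55.8% v 58.6% |
| 0.7 | 71.6% v 74.5% | 72.2% v 74.2% |

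With rs = 1 there is no gain: 55.4% v 55.6% nominal, 54.3% v 54.1% size-matched.

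**The case against.** The strongest reply is that the SAP has a default model and that its trigger looks only at baseline, not at the outcome. SAP 5.1 and 5.4 together could be read as a baseline test at 0.05, and on that reading the rule does almost no statistical harm. This is fair as to size. The link is not written, however: 5.1 names no baseline test, and neither section mentions the model change.

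Taken literally, the trigger could never fire, since no corrected baseline value exists, and the unadjusted model would stand. But the same sentence goes on to add baseline creatinine, so it was evidently meant to operate.

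A reader might infer that the plan inflates type I error. The documents do not support this. Inflation appears only if someone picks the smaller p-value, which the SAP does not license. A reader might also take the 2–17% disagreement as the risk under the plan. That figure counts every trial, including those with similar arms, where adjustment is not permitted.

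Finally, naming either model would close the gap, so adjusting is a preference. That stands in part: the case for adjusting rests on screening creatinine being prognostic.

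**Conclusion.** The concern holds as a gap in specification with a cheap remedy. SAP 5.5.1 does not fix the primary model, its trigger is undefined in both criterion and variable, and imbalance is a poor reason to adjust. A reader might infer that the model was chosen after unblinding; the documents show only that it could be.

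The size is modest and rests on assumed AKI rates, SDs and correlations. A mechanical p<0.05 or p<0.20 rule performs close to the unadjusted model and does not materially inflate type I error. Under a 20% creatinine reduction it leaves about 0.3–2% or 1–6% of all trials, respectively, in which it permits adjustment and the two models disagree; a looser criterion leaves more. Type I error of about 5.5–8% would need misuse of the open criterion. Always adjusting changes nominal power by about 0 to +8 points (size-matched about −2 to +7), with no gain if screening creatinine does not predict AKI. The change should be made, but the gap does not by itself undermine the trial.

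**What to change.** Before unblinding, delete the conditional sentence in SAP 5.5.1 and write:

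> Logistic regression of AKI on treatment and log uncorrected screening creatinine, two-sided 0.05. The unadjusted model is a sensitivity analysis.

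- Use the same model at 72 and 96 hours. The 96-hour endpoint also needs reconciling with the limit of the correction to days 1–3, which is a separate matter.
- In SAP 5.5.2, replace the conditional adjustment with analysis of covariance that always includes the endpoint's own baseline where measured. The switch to a permutation test for clearly non-normal data is another open choice, which this edit does not close.
- Record the change in SAP 7 with its true timing relative to database lock and unblinding.

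If the sponsor prefers the unadjusted model as primary, stating that without conditions also removes the ambiguity. A supportive analysis with the randomisation strata is optional and not part of this point.

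**Cost.** SAP wording only, with no change in N. No patient is lost, because AKI cannot be computed without the screening value and SAP 5.3 already lists its absence as a major deviation. The odds ratio becomes conditional on baseline creatinine, and the SE of its log rises by 0.01–0.10 in simulation A (for example 0.64 to 0.73). If baseline is not prognostic and events are few (about 9), up to about 2 points of size-matched power can be lost.
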